2.1 Primary Endpoints

2.1.1 Safety

Safety of ExAblate will be determined by an evaluation of the incidence and severity of device / treatment related complications from the first treatment day visit through ALL study follow ups. Adverse events (type, frequency, severity) are expected to be similar to those of previous studies using ExAblate TcMRgFUS for Thalamotomy

All AEs will be reported and categorized by investigators as definitely, probably, possibly, or unrelated to the device or procedure and categorized by treatment group / treatment arm.

2.1.2 Effectiveness

Primary effectiveness will be evaluated using a validated, tremor rating scale: the Clinical Rating Scale for Tremors (CRST) for ET subjects, based upon subjects in whom unilateral ExAblate lesioning is attempted (i.e., Intent-to-Treat analysis). The specific study hypothesis is as follows:

At 3-months post-treatment, the treated (contralateral) upper limb CRST subscore (CRST Part-A & B applicable to upper limb) in the ExAblate-treated group will be statistically lower compared to that in the ExAblate sham-treated control group.

Clinical assessments will be made at the following time points: screening, baseline with subjects on confirmed stable medication (at 1-months post screening), and post-treatment at 1 week, 1 month, 3 months, 6 months, and 12 months.

2.1.2.1 Efficacy Assessments

Tremor will be assessed for each treated ET patient using the CRST [85] at baseline following the medications observation period (i.e.: subjects on confirmed stable medication) but before treatment and at post-treatment intervals: 1 month, 3 months, 6 months and 12 months. The validated rating assessment of tremor will be administered by a movement disorder specialist (e.g.: neurosurgeon, or neurologist or physical therapy specialist in movement disorder). The primary measure utilized in this protocol will be a reduction in the treated (contralateral) upper extremity CRST applicable subscores. Additionally, a total/overall tremor score (out of 160 points) will be obtained for each ET patient at each time interval by summing the appendicular and axial scores.

Quality of life will be evaluated using the QUEST assessment. The QUEST is an ET specific assessment of quality of life changes associated with ET. Tröster *et al.*, 2005, developed QUEST as a clinical tool for correlating changes in 30 aspects of tremor severity, social and personal disability, and perception of health. An independent validation study of the QUEST performed by Martinez-Martin *et al.* concluded that most of the psychometric parameters were found to be satisfactory in their ability to assess the impact of ET on the patients' quality of life.

2.2 Secondary Endpoints

The secondary endpoints of the study are as follows:

1. Quality life claims: Questionnaire for Essential Tremor (QUEST) outcome (upper extremity questions) at Months 3 change from Baseline as compared between treatment groups

2. Durability (as measured by QUEST upper arm extremity questions) of the procedure as reflected by the efficacy data through change from baseline measures through Month 12 follow up
3. Subject daily functionalities: as measured by CRST Part-C (subscores) Month 12 as compared to Baseline, and between treatment groups through Month 3.
4. Crossover cohort treatment outcome (perform 1-3 as above for the Crossover cohort)

2.3 Study Hypothesis

The purpose of this study is to determine the safety profile and to test the effectiveness of MRI-guided focused ultrasound thermal ablation of a designated area in the brain of patients suffering from medication-refractory ET, using the ExAblate transcranial system compared to a sham control.

- For ET Patients: a unilateral thermal lesion will be created in the *ventralis intermedius* nucleus of the thalamus [54]

2.3.1 The Hypotheses Tested

- At 3-months post-treatment, the treated (contralateral) upper limb **CRST** applicable subscores of Part-A & B in the ExAblate-treated group will be statistically lower compared to the ExAblate sham-treated limb in the sham-treated group.

Note:

It should be noted that the pre-market submission to the FDA will be performed following the completion of the 12 months follow up visit of last Test Arm subject. This pre-market submission will be performed in full consultation with and approval of the FDA.

2.4 Case Report Form Data

The study data will be collected electronically. This electronic data capture (EDC) system complies with the current guidance of 21 CFR Part 11, Electronic Records and Signatures.

3 DESCRIPTION OF PATIENT POPULATION

3.1 Patient Selection

Patients with confirmed medication-refractory ET as confirmed by screening will be eligible for this study; full copy of subject consent is provided as **Appendix-A** of this protocol.

3.1.1 Inclusion Criteria

1. Men and women age 22 years or older
2. Subjects who are able and willing to give consent and able to attend all study visits,
3. A diagnosis of ET as confirmed from clinical history and examination by a neurologist or neurosurgeon specialized in movement disorder
4. Tremor refractory to adequate trials of at least two medications, one of which should be a first line therapy of either propranolol or primidone. An adequate medication trial is defined as a therapeutic dose of each medication or the development of side effects as the medication dose is titrated.
5. Following the 1-month medication stability period, subject must be on stable medication for tremor
 - a. The 1-Month stability period visit will be 1-month post consent date
6. Vim nucleus of thalamus can be target by the ExAblate device. The thalamic region must be apparent on MRI such that targeting can be performed by measurement from a line connecting the anterior and posterior commissures of the brain.
7. Able to communicate sensations during the ExAblate TcMRgFUS treatment
8. Postural or intention tremor severity score of greater than or equal to 2 in the dominant hand/arm as measured by the CRST rating scale while stable on medication.
9. May have bilateral appendicular tremor
10. Significant disability due to essential tremor despite medical treatment (CRST score of 2 or above in any one of the items 16-23 from the Disability subsection of the CRST: [speaking, feeding other than liquids, bringing liquids to mouth, hygiene, dressing, writing, working, and social activities])
11. Inclusion and exclusion criteria have been agreed upon by two members of the medical team.
12. Subjects on stable antidepressant medications for at least 3 months may be enrolled into this study (i.e., no change in medication drug or dosage for 3 months).

3.1.2 Exclusion Criteria

1. Subjects with unstable cardiac status including:
 - Unstable angina pectoris on medication
 - Subjects with documented myocardial infarction within six months of protocol entry
 - Significant congestive heart failure defined with ejection fraction < 40

- Subjects with unstable ventricular arrhythmias
- Subjects with atrial arrhythmias that are not rate-controlled

2. Subjects exhibiting any behavior(s) consistent with ethanol or substance abuse as defined by the criteria outlined in the DSM-IV as manifested by one (or more) of the following occurring within a 12 month period:
 - Recurrent substance use resulting in a failure to fulfill major role obligations at work, school, or home (such as repeated absences or poor work performance related to substance use; substance-related absences, suspensions, or expulsions from school; or neglect of children or household).
 - Recurrent substance use in situations in which it is physically hazardous (such as driving an automobile or operating a machine when impaired by substance use)
 - Recurrent substance-related legal problems (such as arrests for substance related disorderly conduct)
 - Continued substance use despite having persistent or recurrent social or interpersonal problems caused or exacerbated by the effects of the substance (for example, arguments with spouse about consequences of intoxication and physical fights).

3. Severe hypertension (diastolic BP > 100 on medication)
4. Subjects with standard contraindications for MR imaging such as non-MRI compatible implanted metallic devices including cardiac pacemakers, size limitations, etc.
5. Known intolerance or allergies to the MRI contrast agent (e.g. Gadolinium or Magnevist) including advanced kidney disease
6. Patient with severely impaired renal function with estimated glomerular filtration rate <30 mL/min/1.73m² (or per local standards should that be more restrictive) and/or who is on dialysis;
7. History of abnormal bleeding and/or coagulopathy
8. Receiving anticoagulant (e.g. warfarin) or antiplatelet (e.g. aspirin) therapy within one week of focused ultrasound procedure or drugs known to increase risk of hemorrhage (e.g. Avastin) within one month of focused ultrasound procedure
9. Active or suspected acute or chronic uncontrolled infection
10. History of immunocompromise including those who are HIV positive.
11. History of intracranial hemorrhage
12. Cerebrovascular disease (multiple CVA or CVA within 6 months)

13. Subjects with uncontrolled symptoms and signs of increased intracranial pressure (e.g., headache, nausea, vomiting, lethargy, papilledema).
14. Individuals who are not able or willing to tolerate the required prolonged stationary supine position during treatment (can be up to 4 hrs of total table time.)
15. Are participating or have participated in another clinical trial in the last 30 days
16. Significant claustrophobia that cannot be managed with mild medication.
17. Subjects unable to communicate with the investigator and staff.
18. Presence of any other neurodegenerative disease such as Parkinson-plus syndromes suspected on neurological examination. These include: multisystem atrophy, progressive supranuclear palsy, dementia with Lewy bodies, and Alzheimer's disease.
19. Anyone suspected to have the diagnosis of idiopathic Parkinson's disease. Anyone with the presence of parkinsonian features including bradykinesia, rigidity, or postural instability will be excluded. Subjects who exhibit only mild resting tremor but no other symptoms or signs of PD may be included.
20. Presence of significant cognitive impairment as determined with a score ≤ 24 on the Mini Mental Status Examination (MMSE)
21. Subjects with life-threatening systemic disease that include and not limited to the following will be excluded from the study participation: HIV, Liver Failure, blood dyscrasias, etc.
22. Subjects with a history of seizures within the past year
23. Subjects with presence or history of psychosis will be excluded. Subjects with significant or active mood disorders including depression will be excluded. For the purpose of this study, we consider a significant mood disorder to include any subject who:
 - Scores ≥ 20 on the PHQ-9 questionnaire
 - Is currently under the care of a psychiatrist
 - Is currently participating in cognitive-behavioral therapy
 - Has been hospitalized for the treatment of a psychiatric illness within 12 months
 - Has ever received transcranial magnetic stimulation
 - Has ever received electroconvulsive therapy

24. Subjects with risk factors for intraoperative or postoperative bleeding: platelet count less than 100,000 per cubic millimeter, INR coagulation studies exceeding local institution laboratory standards, or a documented coagulopathy
25. Subjects with brain tumors
26. Any illness that in the investigator's opinion preclude participation in this study.
27. Pregnancy or lactation.
28. Legal incapacity or limited legal capacity.
29. Subjects who have had deep brain stimulation or a prior stereotactic ablation of the basal ganglia
30. Subjects who have been administered botulinum toxins into the arm, neck, or face for 5 months prior to Baseline.
31. Subjects who have an Overall Skull Density Ratio of 0.45 (± 0.05) or less as calculated from the screening CT.

4 INVESTIGATION PLAN

4.1 Study Design Points

4.1.1 Computer Algorithm for Randomization

Randomization will be accomplished using a central computerized system (see also Section 5.5 below) with secure access from the study sites. The investigator will be assigned a password to access the randomization and the site will be trained to maintain the blind. For example, InSightec currently uses randomization routines provided by the Oracle database system which are accessible via the internet using Microsoft ISA (Internet Security and Acceleration). These systems are maintained at InSightec's main office in Haifa, Israel.

It should be noted that:

- 1 - The Core lab assessor and the participating sites will be blinded from each other's databases.
 - Tremor Core Lab Assessor will review all videotaped assessments Baseline through Month 12 and will remain blinded to treatment assignment at all visits. They will be asked if they can guess treatment group assignment at each recording they score in order to assess maintenance of blinding.
 - Additionally, the sites will have a designated individual qualified by training and expertise in movement disorders who will not be aware of the treatment arm assignment for each subject through Month 3 (e.g., Site Blinded Assessor). They will be asked if they can guess

treatment group assignment at each recording through Month 3 in order to assess maintenance of blinding.

- Subjects and site personnel (with the exception of the treating physician) will not be exposed to subject treatment assignment until all the Month 3 assessments are completed. At Month 3, all subjects will be unblinded. At each visit through Month 3, subjects will be asked if they can guess treatment group assignment in order to assess maintenance of blinding.

2 - This randomization procedure and routines are similar to those used for the PMA P110039 that is currently under review (ExAblate body system for the palliation of painful bone metastases).

4.1.2 ExAblate Test Arm Study Design

The randomized ExAblate Test Arm subjects will proceed to the ExAblate treatment. These ExAblate Test Arm subjects will then be followed up for 3-months post-ExAblate treatment to assess the study endpoints at study follow-up: 1day, 1week, 1 and 3 month visits. Subjects will be unblinded after the Month 3 assessments.

All subjects will be followed for 12-months post-treatment to assess the treatment long term safety and durability with study visits at 6 and 12 months.

4.1.3 Sham Arm Study Design

The randomized, ExAblate Sham Arm subjects will proceed to the ExAblate sham treatment. This ExAblate sham treatment procedure will be identical to that of ExAblate Test Arm except the energy output will be disabled. These ExAblate Sham-treated subjects will then be followed up for 3-months post-ExAblate sham treatment to assess study endpoints; study follow-up: 1day, 1week, 1 and 3 month visits.

At the 3-Months time point after all visit evaluation have been performed, all ExAblate Sham-treated subjects will be unblinded and offered cross over to the actual ExAblate treatment as long as they still meet all inclusion/exclusion protocol criteria. They must exhibit a score of 2 or more on at least one of the Month 3 CRST questions 16-23 in order to continue to qualify. All these Crossover Arm ExAblate-treated subjects will be followed according to the same schedule as the ExAblate-treated Arm through the Month 12 post treatment study visit. Subjects may continue to be followed for an annual assessment through 5 years follow-up outside this protocol.

Note: at the time of the pre-Market submission, all available data of this cohort of crossed over subjects will be included in the submission.

4.1.4 Movement Disorders Central Lab Assessments

For this study, the primary efficacy endpoint assessment from Baseline (i.e. immediately post medication observation/stability) through the Month 12 follow up visit will be performed by a central laboratory (Lab). The PI of the central Lab will be a fully trained physician specializing in movement disorders. Core Lab will not be made aware of the study subject's treatment assignment at any time during the course of the study. The purpose of the Tremor Core Lab review is to provide a uniform scoring across all sites.

For this study, each subject's tremor assessment (CRST) will be videotaped at Baseline as well as at each post treatment study visit so that they can be assessed by a blinded central Tremor Core Lab Assessor. The videotapes/Memory cards (e.g.: SD Card) will be de-identified and carefully labeled with the corresponding subject study ID number and sent to InSightec to catalogue and forward to the core lab for scoring. The primary endpoint (mean change from Baseline) at Month 3 will utilize the *Central Lab Blinded Assessor's scoring.*

4.1.5 Videotaping Procedure

The CRST assessments will be videotaped at all visits Baseline through Month 12; Routine Screening CRST video assessments may be obtained and used by core lab as a quality assurance check for videotaping techniques to provide feedback on best taping practices. Screening CRST assessments will not be used in determination of pivotal study endpoints. The goal of the videotaping procedure is to ensure a uniform format to enable the Core Lab assessor to score all subjects utilizing the same filming procedure. This procedure is NOT meant to train assessors how to perform tremor assessment. The CRST assessment will be done by qualified movement disorder specialists.

The videotaping protocol is provided in **Appendix B**. The videotaping protocol should be followed by all sites to provide a standardized format for core lab scoring as well as site scoring utilizing the same sequences. The videotaping protocol provides a suggested sequence grouped by position to minimize discomfort of the subject and relocation of the camera. Additionally, the items are grouped by body region and task for each position.

4.1.5 Data Safety Monitoring Board

A Data Safety Monitoring Board (DSMB) will be used to review all AEs on the study. Their role is to evaluate all AE's that occur throughout the study and provide their assessment of the study safety profile as well as their recommendations for the study continuation. The DSMB recommendations will be communicated to the FDA as part of the annual reporting for this proposed IDE study.

All adverse events will be assessed for their relationship to the study device or procedure. Standard Code of Federal Regulation (CFR) definitions for SAEs and UADEs will be used in assessment of adverse events (see **Section-6.5**).

4.2 Screening Procedures

The following steps are common to all subjects

1. Subjects believed to have medication-refractory ET movement disorder will be offered an Informed Consent to sign prior to further evaluation. Those who accept and sign the consent will be assigned a subject study identification number (ID#).
2. The diagnosis of ET will be confirmed by a neurosurgeon or neurologist specializing in movement disorders, where a comprehensive neurologic examination will be performed, including the screening CRST
3. Medication refractoriness will be defined when tremor persists despite adequate doses of at least trials of appropriate medical therapy. At least one of the medications trialed should be a first line agent, namely propranolol or primidone. The other medication trialed should be a class B agent as defined by the AAN (2005 and 2011 references). Adequate trial (*daily*) dosages are noted below or occur if dose-limiting side effects occur:

First line (class A) tremor therapy:

- Primidone 250 mg
- Propranolol 240 mg
- Propranolol LA 240 mg

Second line (class B) tremor therapy:

- Gabapentin
- Topiramate 400 mg
- Other Beta blockers: Atenolol or Sotalol

Benzodiazepines: Alprazolam or Clonazepam

CT Imaging:

For the purpose of this study, the CT exam should be an Axial scan with bone filter, an image resolution of 512x512, and image thickness of 1mm with zero (0) spacing. This CT imaging will be utilized to compute the Skull Density ratio, and as part of the treatment planning should the subject qualifies for the study.

During this one month “medication observation” phase, the current regimen of medications will be maintained to ensure tremor stability. Screening laboratory and imaging studies will be obtained to complete the enrollment process.

4. A complete medical history will be obtained to determine subject’s general health status; including blood analyses (for PT, PTT, CBC, platelets, and creatinine), and pregnancy urine test for women of childbearing age. Positive test will exclude subjects from study. In the event the pregnancy test is negative, she will be asked to use an acceptable form of contraception throughout entire course of study.

5. PHQ-9 depression will be obtained. All subjects who score ≥ 20 on the test will be excluded from the study.

6. Medication stability and baseline measurements:

In this study, all subjects will be tested again at the one month time point (± 7 days) post screening date. At this visit, the following will be performed:

- Medication stability: subjects will be asked to report any changes in medication taken for tremor consumed over the preceding month.
 - If the subjects do not show stability on medications at 30 days, a second stabilization period may be initiated.
- All those subjects on antidepressants must be on the same antidepressant medication at the same dose for the prior 3 months to be eligible.
- Once the medication stability is confirmed, then all other baseline assessments will be performed:
 - CRST must be performed by a site blinded assessor (SBA) who is proficient in movement disorders. The CRST evaluation must be videotaped for the Central Lab Assessment.
 - QUEST and imaging will also be performed after medication stability has been demonstrated.

7. If at this point it is determined that the subjects **does not** meet all Inclusion and Exclusion criteria and cannot be treated, the subjects will be removed from the study. These subjects will be considered screening failures, and will not be included in any of the safety or efficacy endpoint analyses.
8. If the subject meets all the pre-imaging criteria, then the subjects will be scheduled for the MR .
 - **MR Imaging:** For the purpose of this study, **the following** MR Exams will be performed.
 1. The pre-contrast MR Imaging should include the following:
 - a) T2 Weighted imaging exam along these 2 axes: Axial and Sagittal

8. A second physician specializing in movement disorders will review all the inclusion/exclusion criteria and verify that the subject meets the study screening criteria prior to randomization.

9. Subjects who have been verified as meeting all study criteria may be scheduled for randomization to either the ExAblate Test Arm or ExAblate Sham Arm. The Principal Investigator will log into the random database and obtain the treatment group assignment.

4.2.1 Treatment Procedures

WARNING:

In this study, subject participation is necessary during the course of the ablation procedures. USE OF SEDATIVE MEDICATION MAY IMPAIR COGNITIVE FUNCTIONS OF THE SUBJECT.

However, to alleviate subject anxiety that can develop during a lengthy procedure inside the MR scanner, low dose sedatives like benzodiazepines or dexmedetomidine or equivalent may be administered by slow titration so as to not impair the level of consciousness. Subjects MUST always remain responsive to physician instructions.

Any subject who is not appropriately responsive will not be allowed to continue on with any further treatment procedures until it is deemed clinically safe by the treatment team. Sedation reversal with flumazenil or equivalent may be utilized if excessive sedation occurs. If a subject cannot participate in the treatment after receiving sedation, the procedure will be aborted, and the subject will be considered as screen failure

The following procedure steps would be common to all subjects. Hence, the overall treatment procedure steps will be performed as follows:

Subjects will present to the ExAblate TcMRgFUS treatment center on the morning of surgery “off” medication.

1. An IV line of saline will be positioned for the delivery of fluids and any medications required during the procedure. Some of the subjects may require a urinary catheter to keep the bladder empty during treatment. Noninvasive monitoring of heart rate, blood pressure, systemic oxygen saturation, electrocardiogram, and end-tidal CO₂ will be maintained throughout the procedure using standard MR-compatible monitoring devices.
 - The anesthesiologist, or nurse anesthetist, or treating physician will be present to monitor subject's overall well being. Their major role is to monitor and control of blood pressure to prevent hypertension during the procedure. Subjects must be able to communicate during the entire procedure, and must be able to operate the stop sonication button.
 - To address emergency situations should they occur, a standard ventilator should be available in close proximity to the MR scanning room; per local site clinical standards.
2. The subject's head will be carefully shaved and examined for pre-existing scalp scars or any other scalp lesions.
3. Graduated compression stockings will be worn to prevent deep venous thrombosis in the lower limbs.

4. The subject's head will be placed in the stereotactic head frame (similar to those used in stereotactic surgery and radiotherapy) for use during the actual ExAblate TcMRgFUS treatment.
5. Subject will be positioned supine and headfirst on the MR/ExAblate therapy table.
6. The half-spherical helmet containing the elements of ExAblate transducer will be positioned around the subject's head in the treatment position. This should be done according to measurements taken from the pre-operative/imaging session(s).
7. An elastic membrane will be attached to the Subject's head and to the transducer to create the acoustic coupling system between the ultrasound transducer and the scalp.
8. The immobilization system will be secured over the subject head to maintain a constant relationship between the target and the transducer.
9. A baseline assessment of symptoms of tremor will be obtained before the ablation procedure begins
10. The interface between the scalp and the transducer (within the elastic membrane) will then be filled with degassed water. This volume will be completely filled with care to avoid air bubbles between the face of the transducer and the scalp. Through active circulation and cooling system, the water will be maintained chilled throughout the procedure to avoid undesired heating of the scalp and skull.
11. A 3D localizer MR scan will be obtained to allow further refinement of the position of the ExAblate transducer focal point with respect to the targeted zone.
12. A series of MR images will be acquired to identify the target area, and plan the actual treatment
 - o T2 Weighted imaging exam along at least 2 axes: Axial and Sagittal
13. The pre-therapy MRI and CT image datasets will be registered to the T2 weighted MR images that were just acquired. This image fusion of pre-operative MR assists in the accurate delineation of the target area and determination of a safe sonication pathway
 - o The fusion of the CT data is required for the computation of phase correction values to correct for skull aberration, and identification of intracranial calcifications
 - o Scars of the scalp will be designated to ensure the ultrasound beam avoids these specific areas
14. The treatment volume and plan will be defined by the neurosurgeon. The ExAblate TcMRgFUS system will automatically compute the number of sonications, and the (per sonication spot) phase and amplitude corrections necessary for the system to produce a focal spot at each of the desired locations.

At this stage, all those subjects who do not meet the MR requirement will be considered screen failures.

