6.1 General Procedure Related Risks

6.1.1 Risk of Magnetic Resonance Scanners:

MRI has no known deleterious biological effects in subjects with no contraindications. The incidence of claustrophobia during MRI examinations is approximately 10-15%. All subjects exhibiting claustrophobia will be exited from the study.

6.1.2 Risk of Intravenous (IV) Catheter:

There is a potential risk from the IV catheter used during the procedure. Participants can expect a small amount of pain and/or bleeding/bruising at the IV site. There is a small risk of infection. This procedure will follow the ‘standard of care’ at the study site.

6.1.3 Risk of Urinary Catheter:

There is a potential risk if a urinary catheter is used during the treatment. Participant may expect varying levels of Urinary Tract Infection due to the use of the urinary catheter. In a different study for the ExAblate treatment of uterine fibroid (Pivotal study under IDE G020001 that lead to PMA approval under PMA # P040003), the incidence of this risk was found not to exceed 3.7%. This procedure will follow the “standard of care” at the study site.

6.1.4 Risk of Stereotaxic Head Frame:

In this study, the Integra Radionics frame will be used for all treatments. The main part of this frame is a metal based ring that serves as a base for the rest of the fixation components. This frame comes with non-metallic posts mounts. Into the non-metallic post mounts, accompanying nylon encapsulated screws with a metallic tip are fitted through the posts. Only the metal tip of the screw is in contact with the patient. The risk of any skin event at or in the vicinity of the metallic tips is mitigated by the fact that the screws outer shell are out of nylon, and therefore eliminates any electrical conductivity to the skin. This is further mitigated by the fact that these screws are mounted on the non-metallic posts that links them to the metallic ring. Hence, the Integra frame is actually manufactured and sold with built in mitigating steps aimed at reducing / eliminating skin event risks. When the full set up is completed, the metallic ring is NOT in contact with the patient.

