5.1 Safety Analysis Population

The Safety analysis population will include all randomized subjects who received at least one sonication – ExAblate or Sham – in the Main stage of the study, as indicated by the following:

- CRF field "Number of Performed Sonifications" on the ExAblate Treatment Form has a value of at least one
or
- At least one CRF field “Sonication Duration [sec]” on Sonication Form has a value greater than zero.

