5.2 Efficacy Analysis Populations

5.2.1 Intent to Treat (ITT)

The ITT analysis population will include all Safety subjects for whom there exist valid baseline measurement and at least one post-baseline measurement on the primary efficacy data.

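### Protocol 6.1.1 exits every claustrophobic subject although exclusion 16 and 4.2.1 allow medication, and the screen-failure label in 4.2.1 can fall on a randomized subject

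*Protocol*

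**What the plan says.** **Claustrophobia and anxiety.** Exclusion 16 (Protocol 3.1.2) bars "Significant claustrophobia that cannot be managed with mild medication". Protocol 4.2.1 warns that sedatives may impair cognition, then allows for anxiety in the scanner that "low dose sedatives like benzodiazepines or dexmedetomidine or equivalent may be administered by slow titration so as to not impair the level of consciousness". Protocol 6.1.1 puts claustrophobia at about 10-15% of MRI examinations and adds: "All subjects exhibiting claustrophobia will be exited from the study".

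**Aborts after sedation.** Under 4.2.1, if a sedated subject cannot take part, "the procedure will be aborted, and the subject will be considered as screen failure". The list of common treatment-day steps in 4.2.1 ends by also making screen failures of subjects who do not meet the MR requirement.

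**Assignment.** Step 9 of Protocol 4.2, before the treatment procedures, says of eligible subjects: "The Principal Investigator will log into the random database and obtain the treatment group assignment". Sections 4.2.1.1 and 4.2.1.2 then describe sonications for subjects randomized to each arm.

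**Who is analyzed.** Step 7 of Protocol 4.2 says that screening failures "will not be included in any of the safety or efficacy endpoint analyses". SAP 5.1: "The Safety analysis population will include all randomized subjects who received at least one sonication", ExAblate or sham. SAP 5.2.1 builds on that: "The ITT analysis population will include all Safety subjects for whom there exist valid baseline measurement" and at least one later measurement.

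**The concern.** Two things go wrong. First, a subject whose claustrophobia responds to mild medication may be enrolled under 3.1.2 and sedated and treated under 4.2.1, yet must leave the study under 6.1.1. Sites could handle the same subject differently.

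Second, screen failure is a pre-randomization status, but 4.2.1 applies it on the treatment table with no such limit. If it reaches a randomized subject, an exclusion is made after assignment. The treating physician is not blind to arm (Protocol 4.1.1). Sham table time is capped by default at 1 h 30 min (4.2.1.2), while exclusion 14 allows for up to 4 hours on the table, so such aborts could differ between arms. Safety is a primary endpoint counted from the first treatment day (2.1.1), and an abort after sedation is a case in which a procedure-related event may have occurred.

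**Working it through.** The plan states no figure for this point, so the check is mainly a comparison of texts.

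**1. Claustrophobia that mild medication controls**

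| Text | Result |
|---|---|
| Exclusion 16 | Eligible |
| 4.2.1, if it shows as anxiety during the procedure | Low-dose sedation, treatment continues |
| 6.1.1 | Exited |

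The first two agree; the third has no severity or medication qualifier and contradicts them.

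For scale only, apply the 10-15% of 6.1.1 to the 72 to 80 randomized subjects of 5.4: 0.10 × 72 = 7.2 and 0.15 × 72 = 10.8; 0.10 × 80 = 8 and 0.15 × 80 = 12. This is an upper range. The rate is for MRI examinations in general, and these subjects have already passed exclusion 16 and a baseline MR.

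**2. Abort after sedation, by timing**

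| Moment of abort | Assigned? | Protocol 4.2.1 | SAP |
|---|---|---|---|
| On the table, if assignment has not yet been obtained | No | Screen failure | In no set, correctly |
| After assignment, before any sonication | Yes | Screen failure | Neither Safety nor ITT |
| After at least one sonication | Yes | Screen failure | In Safety; in ITT if baseline and a later value exist |

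The third row does not depend on when a site logs in. Sonications differ by arm, so assignment must come before the first one. Section 4.2.1 also reaches into that phase: it covers anxiety arising in the course of a long procedure and bars unresponsive subjects from further treatment steps. In that row the label conflicts with SAP 5.1. It also sits badly with the protocol's own ITT basis, which is attempted lesioning (2.1.2 and 5.2).

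For the second row, SAP 10.1 builds its list of subjects excluded from analysis sets on the Safety population, so a subject without a sonication cannot appear there. Its screen-failure listing specifies a reason but no arm or adverse events.

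**3. What one lost subject does to safety**

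Protocol 5.4 gives 0.95 as the chance of seeing a 5% event in 60 subjects: 1 - 0.95^60 = 0.954, which reproduces it. With 59 subjects, 1 - 0.95^59 = 0.952. Detection probability barely moves. If the lost subject had an event, the ExAblate rate is understated by about one subject in 54 to 60 (3/4 of 72 and of 80): 1/60 = 1.7% to 1/54 = 1.9%.

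**4. Bound on efficacy**

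Section 18 of the long-term follow-up protocol reports 56 ExAblate and 20 sham ITT subjects: 56 + 20 = 76. The ceiling in 5.4 is 80, so 80 - 76 = 4. Put all four in ExAblate with 0% improvement: 46.9 × 56/60 = 43.8%. Sham is -0.1%, with an upper 95% limit of 9.5%.

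**The case against.** The strongest reply is that 4.2.1 does not give randomization status. Step 9 says that subjects may be scheduled for randomization, and the MR screen-failure sentence shows that screening stays open through on-table planning. Some sedation aborts may therefore precede assignment. This stands, and it rules out reading every such abort as a randomized subject. It does not help once sonications have begun.

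A reader might also infer that the protocol removes these subjects from all safety and efficacy analyses. Step 7 is written for subjects who fail eligibility at screening, and nothing expressly extends it to treatment-day aborts. It is, however, the only consequence the protocol attaches to the label. Protocol 5.8 leaves analysis detail to the SAP, and SAP 5.1 already keeps anyone randomized with a sonication. Investigators must document all adverse events (6.6) and the DSMB reviews them (6.7). What can go missing is a subject's place in the safety tables, not the record of the event.

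Leaving out subjects with no sonication is a general modified-ITT choice and not a sedation defect. That is fair; the gap is only that they are not accounted for by arm.

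Two further inferences are not supported. Section 6.1.6 credits the avoidance of sedatives, but as a reason why thrombosis risk is low; it is not an operating rule that forbids what 4.2.1 allows. Nor can it be said that consent omits sedation risk, because the consent form is not in the text available for review.

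**Conclusion.** The point holds and is minor. The contradiction between 6.1.1 and exclusion 16 with 4.2.1 is plain on the page. The screen-failure label is a post-randomization exclusion whenever the abort comes after assignment, and it conflicts with SAP 5.1 whenever a sonication has been given.

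The number affected is not given. A reader might take 7 to 12 exits from the 10-15% rate, but that rate does not describe subjects already screened for claustrophobia. The reported ITT set leaves room for at most 4 losses for any reason, assuming that no aborted subject went uncounted as randomized. The Month 3 efficacy conclusion is not at risk: 43.8% against -0.1% in the bounding case. The gain from a change is consistent site conduct and complete safety accounting.

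**What to change.** 1. Protocol 6.1.1: replace the exit sentence with the exclusion 16 rule, and refer to 4.2.1 for anxiety on the treatment day.
2. Protocol 4.2.1: in the sedation sentence and in the MR-requirement sentence that closes the common steps, limit screen failure to subjects not yet randomized. After randomization, record the procedure as not completed, with the reason, and continue adverse-event follow-up on the existing schedule. This works whenever a site obtains the assignment.
3. SAP 10.1: list randomized subjects with no sonication by arm, with reason and adverse events. SAP 5.1 needs no change.
4. Optional: correct the clause on avoidance of sedatives in Protocol 6.1.6 so that it agrees with 4.2.1.

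The cost is about three protocol sentences (a fourth if item 4 is taken up) and one SAP listing. No new visits are needed.
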